6 SUBJECT DISPOSITION

Subject disposition will include the number of subjects screened, number of randomized subjects, number and percentage of subjects in each analysis population, number and percentage of subjects completing the scheduled treatment of investigational products, number and percentage of subjects completing the study treatment period up to Week 52, and number and percentage of subjects completing the study follow-up period up to Week 76 by treatment arm and by study stage.

The number and percentage of subjects discontinuing early from the study will be summarized for primary reasons of discontinuation. Also, the number and percentage of screening failures will be summarized for primary reasons of ineligibility in a separate table.

Disposition status will be listed for all subjects.

7 PROTOCOL DEVIATIONS

Protocol deviations (PD)s will be identified during the study, evaluated and categorized as Critical, Major or Minor before the database lock. Following process improvement measures to external Contract Research Organization) Clinical Trial Management System for tracking, processing and classification of PDs, classification terms for PDs changed for PDs processed after the 16May2022. In order to ensure a consistent unified categorization of PDs, will re-map PDs categorized after 16May2022 to the original categories used prior to the change in classification categories.

The type of protocol deviations will be summarized by treatment arm for each stage and overall.

8 DEMOGRAPHY AND MEDICAL HISTORY

8.1 Demographic and Baseline Characteristics

Demographic and baseline characteristics including sex, race, ethnicity, age, age group (<65 versus >= 65 years old), height, weight and body mass index will be summarized by treatment arm and study stage (individually and combined). Baseline pregnancy test, time since diagnosis of post-polio syndrome(years), time since diagnosis of poliomyelitis(years), IgA levels, IgA antibodies, general health assessment and blood assessment for general health, immunologic function, and viral exposure will be summarized.

Time since diagnosis of post-polio syndrome will be calculated as:

(Subject ICF date – date of diagnosis of post-polio syndrome)/365.25

Time since diagnosis of poliomyelitis will be calculated as:

(Subject ICF date – date of diagnosis of poliomyelitis)/365.25

All demographic and baseline characteristics data will be listed.

8.2 Medical History

Medical history events will be coded using Medical Dictionary for Regulatory Activities (MedDRA) dictionary version 17.1 and summarized by treatment arm, system organ class (SOC) and preferred term (PT).

9 CONCOMITANT MEDICATION AND TREATMENT

9.1 Prior and Concomitant Medication

All medications as documented by the investigator will be coded using ATC classification codes via the World Health Organization Drug classification Dictionary (WHO-DD). All medications will be summarized by treatment arm and sorted alphabetically by medication class (i.e., ATC level 1) and medication sub-class (i.e., ATC level 3). If the ATC level 3 term is missing, the ATC level 2 term will be used in the medication summary table and data listing.

The following convention will be used for missing or partial end date information in order to determine whether a medication is prior or concomitant:

The unknown portions of a medication end date will be assumed to be as late as possible. If a medication end date is incomplete but the month/year of medication end date is prior to the month/year of the start of study treatment, then the medication will be considered a prior medication. If a medication end date is incomplete but the month/year of medication end date is the same as the month/year of the start of study treatment, then the medication will be considered a concomitant medication. All other incomplete medication end dates and all medications with missing end dates will be assumed to be concomitant medications. Start/end

dates reported in the eCRFs will be presented in the listings. Further details of the imputation methods for partial dates is provided in section 12.1.2.

Prior medications are defined as any medication ended prior to the start of study treatment (i.e., start of the first study infusion at Week 0).

Concomitant medications are defined as any medication started on or after the start of study treatment or any medication taken prior to the start of study treatment and continued after the start of study treatment during the study.

9.2 Treatment Compliance

Treatment volume compliance will be calculated as total volume infused * 100% / total volume prepared during the study. The total volume prepared and dispensed by pharmacist is the intended dose volume a subject should be given based on the body weight.

Treatment infusion compliance will be calculated as the number of actual infusions * 100% / number of infusions expected or planned.

The treatment compliance and infusion compliance will be listed and summarized by treatment arm and study stage. Overall compliance (treatment compliance x infusion compliance) will be listed and summarized by treatment arm and study stage. The number of subjects with compliance between 80% and 120% will be calculated.

9.3 Treatment Exposure

For each treatment, the duration of exposure (weeks), number of infusions received, and the total volume infused in liters will be summarized. Duration of exposure is determined by calculating the difference between the start date of last infusion and the start date of first infusion inclusive divided by seven to give the value in weeks [(start date of last infusion—start date of first infusion) +28]/7, rounding to one decimal place.

10 EFFICACY ANALYSES

Analysis will be performed for each individual stage for the primary endpoint (2MWD) only and the significance of the treatment effect at each stage will be combined to provide an overall assessment of treatment efficacy. For secondary and exploratory endpoints, analyses will be performed over the two stages combined, using the placebo and selected dose of Flebogamma[®] 5% DIF treatment groups only.

Efficacy analyses will be performed on the ITT population. The ITT analyses will be performed according to the treatment randomized, not the actual treatment received. The primary efficacy analyses will also be performed on the PP population.

10.1 Primary Efficacy Analyses

The primary efficacy variable is physical performance (2MWD) from baseline to the end of the treatment period (Week 52). The primary efficacy variable will be analyzed to compare each active treatment arm to placebo at Week 52 by using mixed-effect model repeated measures (MMRM) method separately for each stage.

The MMRM will include change from baseline in 2MWD as the dependent variable; treatment, protocol-specified visits, treatment-by-visit interaction, and main part of the body affected (lower extremity versus upper extremity) as the fixed effects; baseline 2MWD measure as a covariate; and measures within-subject at each visit as a repeated measure. covariance matrix will be assumed to be unstructured. If the procedure does not converge then a compound symmetric variance-covariance matrix will be used instead.

The least-squares means for each treatment arm and its differences along with p-values between Flebogamma® 5% DIF and placebo at Week 52 will be estimated separately for each stage. The sample SAS® code for MMRM model is below:

```
proc mixed data=pp method=ml;
   class Subject Treatment Visit Bodypart;
   model change = Baseline Bodypart Treatment Visit
                  Treatment*Visit / s;
   repeated Visit / type=un subject=Subject r;
   lsmeans Treatment*Visit / pdiff cl;
run;
```

The overall adjusted p-value for the selected dose of Flebogamma® 5% DIF vs placebo at Week 52 will be calculated from the p-values of both Stage 1 and Stage 2 by the method proposed by Posch & Bauer (2005) in order to control the overall type I error rate for testing the equal means between the selected dose and placebo:

```
H_0: \mu_{flebogamma} - \mu_{placebo} = 0 (or equivalently H_0: \mu_{flebogamma} = \mu_{placebo})
```

versus

```
H_A: \mu_{flebogamma} - \mu_{placebo} \neq 0 \; (\mu_{flebogamma} - \mu_{placebo} > 0 \; or \; \mu_{flebogamma} - \mu_{placebo} < 0)
```

where $\mu_{flebogamma}$ and $\mu_{placebo}$ are the mean change of 2MWD for the selected Flebogamma[®] 5% DIF dose group and placebo respectively. The superiority will be deemed to have been demonstrated if the two-sided overall adjusted p-value is less than or equal to 0.05 and $\mu_{flebogamma} - \mu_{placebo} > 0.$

Let's assume two active arms A and B (corresponding to 1 g/kg and 2 g/kg of Flebogamma[®] 5% DIF, respectively) comparing to Placebo in Stage 1 with one active arm (arm B) moving into Stage 2 without loss of generality. Let's denote p_A and p_B as the one-sided p-values in Stage 1 comparing to placebo for treatment A and B, respectively; q is the one-sided p-value in Stage 2 comparing B to placebo; p_{AB} and q_{AB} are the one-sided p-values for testing null hypothesis H_{AB} (i.e., the intersection hypothesis $H_A \cap H_B$) for Stage 1 and Stage 2, respectively. As demonstrated in the paper (Posch & Bauer; 2005) example,

$$p_{AB} = min(2 p(1), p(2)),$$
 for ordered p-value $p(1) \le p(2)$ (Simes test) and $q_{AB} = q$.

By using the weighted inverse normal combination function, the combination function is:

$$C(x, y) = 1 - probnorm(v*probit(1-x)+w*probit(1-y)),$$

where $v=sqrt(n_1/(n_1+n_2))$ and $w=sqrt(n_2/(n_1+n_2))$, n_1 and n_2 are sample size for Stage 1 and Stage 2 for the selected arm and placebo.

The overall adjusted one-sided p-value for hypothesis H_B (i.e., overall efficacy) would be:

Overall adjusted one-sided p-value =
$$max(C(p_{AB}, q), C(p_B, q))$$
.

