10.3 Level of significance

For 1-sided statistical tests, an alpha level of 0.025 will be considered to indicate statistical significance. For 2-sided statistical tests, an alpha level of 0.05 will be considered to indicate statistical significance.

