2 INTRODUCTION

This Statistical Analysis Plan (SAP) is based on Protocol IG1104 Version 7.0, dated March 7th, 2022.

Subsequent to the finalization of the protocol, Instituto Grifols S.A. took the decision to prematurely terminate this trial once subjects participating at the time of the decision had completed their study treatment. The early termination resulted from a business decision by Grifols, with no safety concerns regarding the Investigational Product and no changes in the risk/benefit for ongoing subjects participating in the study.

As a commitment to study participants, all subjects that were enrolled at the time of the decision were given the opportunity to complete blinded study drug infusions, continue with treatment visits and be assessed as per protocol. In addition, where feasible and consented by study subject, assessments and procedures to be performed during an early discontinuation visits were to take place after the last investigational product infusion on infusion visit 13. Alternatively, subjects in the follow-up period were to be discontinued as soon as possible.

The purpose of this SAP is to ensure that the statistical methodologies that will be used, and the data listings, summary tables and figures which will be produced, are appropriate and complete to support valid conclusions regarding the study objectives and the completion of Clinical Study Report (CSR).

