5.3 Sample Size Considerations

The sample size of this clinical study has been calculated based on the primary efficacy endpoint (2MWD) at the end of the treatment period.

Baseline measure of 2MWD in patients with PPS has been estimated in about 120 meters with standard deviation

s between 24 and 28 meters. The standard deviations for change from baseline to week 3 and week 17 in 2MWD are in the range of 8 to 11 meters [Horemans HL, Nollet F, Beelen A, et al., Stolwijk-Swüste JM, Beelen A, Lankhorst GJ, et al., Horemans HL, Beelen A, Nollet F, et al]. In order to show the superiority of Flebogamma® 5% DIF over placebo, an effect size of 5% (6 meters) in change from estimated baseline in 2MWT (120 meters) is assumed.

A clinically relevant change in distance walked at the end of the treatment period (after 52 weeks of treatment) between groups (Flebogamma[®] 5% DIF versus placebo) has been stated to be 5%.

In order to show the treatment difference of 6 meters in 2MWD with a standard deviation of 11 meters, 99 subjects need to be randomised into one of three treatment arms in Stage 1 and 66 subjects need to be randomised into one of two treatment arms in Stage 2. To account for a 20% dropout rate, approximately 126 will be randomised into one of the three treatment arms (42 subject/arm) in Stage 1, and approximately 84 subjects will be randomised into one of the two treatment arms (42 subject/arm) in Stage 2.

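### The MMRM fallback in SAP 10.1 is homogeneous compound symmetry, which averages the Week 52 variance over visits; if the SD of change grows, the stage-wise test is liberal, and a fallback keeping a separate Week 52 variance avoids this cheaply.

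*SAP*

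**What the plan says.** SAP 10.1 analyses change in 2MWD separately in each stage with an MMRM. On the within-subject structure it says "covariance matrix will be assumed to be unstructured", followed by a single contingency: "If the procedure does not converge then a compound symmetric variance-covariance matrix will be used instead". The sample code has "proc mixed data=pp method=ml" and "repeated Visit / type=un subject=Subject r". It requests no empirical standard errors and names no heterogeneous structure.

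The Week 52 p-value from each stage goes straight into the weighted inverse-normal combination later in SAP 10.1. SAP 10.2 and 10.3 reuse the model on pooled data, and 10.4 uses an MMRM as well. Protocol 10.1.2.1 names no covariance structure.

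The visit factor is described only as the visits specified in the protocol. Protocol 4.5.2.14 schedules 2MWD after baseline at Weeks 12, 24, 36 and 52 on treatment and at Weeks 64 and 76 in follow-up.

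**The concern.** Homogeneous compound symmetry assumes equal variance at every visit and equal correlation between every pair of visits. A change from baseline followed for a year may well become more variable with time. If it does, the Week 52 comparison borrows a smaller variance from the earlier visits, its standard error is too small, and the stage-wise p-value is too small. The combination test takes that p-value as given, so nothing downstream corrects it.

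The SAP also moves in one step from the most flexible structure to a very restrictive one, although intermediate structures with a separate Week 52 variance exist.

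The trigger needs some attention because of early termination. SAP 2 says: "Alternatively, subjects in the follow-up period were to be discontinued as soon as possible". If Weeks 64 and 76 belong to the model, they could be thinly filled, and sparse cells are where an unstructured fit is most likely to fail.

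**Working it through.** **The plan's own figures.** The plan states no error rate for the fallback, so there is none to reproduce. Its sample size, which sets the stage size used here, does reproduce: 33 evaluable per arm and 20% dropout give 33/0.80 = 41.25, rounded up to 42 per arm, hence 126 in Stage 1 and 84 in Stage 2.

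**Inputs.**
- Nominal level: two-sided 0.05, or one-sided 0.025 on the scale of the combination test (Protocol 10.3).
- SD of change: the only figures are in Protocol 10.2 and SAP 5.3. "The standard deviations for change from baseline to week 3 and week 17 in 2MWD are in the range of 8 to 11 meters". The planning SD is 11 m.
- SD at Weeks 12, 24, 36 and 52: not given. Every path below is an assumption.

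**Formula.** With complete data, compound symmetry bases the Week 52 standard error on the mean of the visit variances. The ratio of the reported to the correct SE is r = sqrt(mean visit variance / Week 52 variance), and the actual two-sided error is 2 × (1 − Φ(1.96 r)).

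**Worked case.** SDs of 8, 9, 10, 11 m give a mean variance of (64 + 81 + 100 + 121)/4 = 91.5. Then r = sqrt(91.5/121) = 0.87, and 1.96 × 0.87 = 1.70, so the error is 8.8%.

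| SD at Weeks 12, 24, 36, 52 (m) | r | Two-sided error |
|---|---|---|
| 11, 11, 11, 11 | 1.00 | 5.0% |
| 9.9, 11, 11, 11 | 0.98 | 5.6% |
| 10 rising evenly to 11 | 0.96 | 6.1% |
| 8, 11, 11, 11 | 0.94 | 6.6% |
| 8, 9, 10, 11 | 0.87 | 8.8% |
| 8, 10, 12, 14 | 0.80 | 11.6% |
| 11 falling evenly to 9 | 1.11 | 2.9% |
| 11, 10, 9, 8 | 1.20 | 1.9% |

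The second row reads the plan's range as growth at its own time points: 8 m at Week 3 and 11 m at Week 17 gives 8 + 3 × 9/14 = 9.9 m at Week 12, then a plateau at the planning SD.

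**Simulation under no effect.** The SAP model was fitted to 3,360 replicates at planned size with the 8, 9, 10, 11 m path (Monte Carlo SE about 0.4 points).

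| Setting | Compound symmetry, Stage 1 / Stage 2 | Unstructured, Stage 1 / Stage 2 |
|---|---|---|
| ML, 20% dropout | 9.7% / 9.3% | 5.5% / 5.5% |
| REML, 20% dropout | 9.2% / 8.6% | 5.0% / 5.1% |
| ML, no dropout (33 per arm) | 9.3% / 10.0% | 5.1% / 5.7% |
| ML, serial correlation | 10.4% / 10.1% | 5.6% / 4.9% |

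In the first setting, if both stages fall back, the combined one-sided error with dose selection is 5.5%, against 2.7% for the unstructured fit.

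**If Weeks 64 and 76 are in the model.** With all six visits equally filled:
- SD continuing to 12 and 13 m: mean variance 679/6 = 113.2, r = 0.97, error 5.8%.
- SD flat at 11 m after Week 52: 608/6 = 101.3, r = 0.92, error 7.3%.

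If the follow-up cells are only one tenth filled, weighting the visits by how full they are gives (366 + 0.1 × 313)/4.2 = 94.6 and (366 + 0.1 × 242)/4.2 = 92.9. The approximate errors are 8.3% and 8.6%.

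**Covariance parameters.** Four visits need 4 × 5/2 = 10; six need 6 × 7/2 = 21.

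**The case against.** The strongest reply is that both links in the chain are uncertain.

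- **SD path.** The 8 to 11 m range belongs to Weeks 3 and 17 and is not presented as a time trend. A reader might infer that the fallback doubles the error rate. The documents do not support that: it needs a Week 12 SD of about two thirds of the Week 52 SD. Reading the range at its own time points gives 5.6%, and a falling SD makes the test conservative. This stands.
- **Trigger.** With 10 parameters and 84 to 126 subjects, non-convergence looks unlikely, and its probability has not been estimated. The six-visit model that makes failure more plausible also dilutes the inflation if follow-up is well filled. SAP 5.1 moves termination visits to the next scheduled visit, and the Early Discontinuation Visit includes 2MWD (Protocol 5.3), so subjects stopped in follow-up could still supply Week 64 or 76 values. This stands in part: how full those cells are is not stated, and where they are sparse most of the inflation remains.
- **Visibility.** A reader might infer that the problem would pass unseen. It would not: the switch is written into the SAP, and the Week 52 ANCOVA in SAP 10.2 has a residual variance that is not pooled over visits, so it offers a comparison. But that ANCOVA is a sensitivity analysis on pooled data and does not replace the stage-wise p-values.

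**Conclusion.** The concern holds as a conditional weakness in a contingency rule. If the fallback is used in a four-visit model, the stage-wise two-sided error is 5.0% with constant SD, about 5.6 to 6.6% with modest or early growth, and about 9 to 10% with growth from 8 to 11 m between Weeks 12 and 52. It is below 5% if the SD falls. Steeper growth would give more, and well-populated follow-up visits less.

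These figures rest on assumed SD paths, model-based standard errors and, in the simulation, the planned stage size. They are conditional on the fallback being used, so they do not show that the trial's error rate is wrong: with the unstructured model, the simulated stage-wise rate was about 5 to 6%. The case for acting is that the rule can give a wrong error rate exactly when it is needed, and that changing structure after a failed fit on unblinded data would be data-driven.

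**What to change.** In SAP 10.1:

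1. State that the primary MMRM uses Weeks 12, 24, 36 and 52 only. This also removes the most plausible cause of non-convergence.
2. Replace the compound-symmetry sentence with an ordered list of structures that keep a separate Week 52 variance: heterogeneous Toeplitz, then heterogeneous AR(1), then heterogeneous compound symmetry. Use the first that converges.
3. Apply the same order to the models in 10.2 to 10.4.

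Small-sample-corrected sandwich standard errors may be added but are optional, since a heterogeneous structure already removes the averaging.

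The cost is a few lines of SAP text and code and a few more covariance parameters in the fallback. The planned unstructured analysis keeps its covariance structure. The change should be made before unblinding.

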- 19. Subjects with renal impairment (*i.e.*, serum creatinine exceeds more than 1.5 times the upper limit of normal [ULN] for the expected normal range for the testing laboratory).
- 20. Subjects with AST or ALT levels exceeding more than 2.5 times the ULN for the expected normal range for the testing laboratory.
- 21. Subjects with hemoglobin levels <10 g/dL, platelets levels <100,000/mm³, white blood cells count <3.0 k/ μ L and ESR >50 mm/h or twice above normal.
- 22. Subjects with known seropositive to HCV, HIV-1 and/or HIV-2.
- 23. Subjects with a history of intolerance to fructose.

CDIECIS	Number	GLB-PRT-FLB-IG1104	Version	7.0	Status	Effective	Effective Date	07-Mar-2022
CIVILO	IG1104 - A I	multicenter, prospective, randomized, placebo-controlled,	double-blind	, parallel-gro	up clinical trial t	to assess the efficacy		70.3-01
Bioscience Industrial Group	and safety c	of Immune Globulin Intravenous (Human) Flebogamma® 5	5% DIF in pat	tients with Pc	ι Post-Polio Syndπ	ome	rage	18 01 122

Analytical Plan/Statistical Method:

Demographic and baseline characteristics will be summarized using descriptive statistics.

Efficacy analyses will be primarily run on the intent-to-treat (ITT) population. In addition, for sensitivity analysis, efficacy analyses will also be run on the per protocol (PP) population.

The ITT population will include all randomized subjects. Subjects will be analyzed per the assigned randomized treatment.

The PP population will include subjects in the ITT population who have received at least 8 infusions, without having 2 consecutive missed infusions, of any investigational product (test or placebo) during the treatment period, have baseline and at least 1 post-baseline measure of the 2MWD, and have no major protocol violations that might have impact on the primary efficacy endpoint (as determined at a data review meeting prior to database lock and unblinding).

The primary efficacy endpoint is physical performance, evaluated by 2MWD, from baseline (at EV/IV1) to the end of the treatment period (at EoTV, Week 52) for Flebogamma[®] 5% DIF compared to placebo in the ITT population.

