10.1.2 Statistical analysis of efficacy

Efficacy analysis will be primarily based on the intent-to-treat (ITT) population (see Section 10.6.1). In addition, for sensitivity analyses, efficacy analyses will also be run on the per protocol (PP) population (see Section 10.6.1).

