10.6 Selection of subjects to be included in the analyses

10.6.1 Population for statistical analysis of efficacy

Two study populations for statistical analysis of efficacy may be used: ITT population and PP population. All efficacy analysis will be primarily run on the ITT population and then they may be run on the PP population.

The **ITT population** will include all randomized subjects. Subjects will be analyzed per the randomized treatment.

The **PP population** will include subjects in the ITT population who have received at least 8 infusions, without having 2 consecutive missed infusions, of any investigational product (test or placebo) during the treatment period, have baseline and at least 1 post-baseline measures of the 2MWD, and have no major protocol violations that might have impact on the primary efficacy assessment (as determined at a data review meeting prior to database lock and unblinding).

The major protocol violations will include, but are not limited to, the following: entry inclusions/exclusions not met, more than 1 consecutive missed infusion or more than 4 missed infusions during the treatment period, randomization error (*i.e.*, wrong treatment received), and treatment unblinded during the study treatment period.

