10.2 Primary Efficacy Sensitivity Analyses

The analysis outlined in section 10.1 will be repeated using the PP population. The following additional sensitivity analyses will be performed for the ITT population, using placebo and selected dose of Flebogamma[®] 5% DIF 2MWD data from Stages 1 and 2 combined.

- 1. An MMRM using the same model used in the primary analysis. Least squares (LS) means and 95% CIs will be presented and plotted by visit and treatment group.
- 2. An analysis of covariance (ANCOVA) will be performed with change in 2MWD from baseline to 52 Week as the dependent variable, treatment and main part of the body most significantly affected (lower/upper extremities) by PPS as the fixed effects, and baseline 2MWD measure as covariate. Data missing at 52 Week will be imputed using the Last (post-baseline) 2MWD Observation Carried Forward [LOCF]. LS means and 95% CIs for treatment effect and treatment comparison at week 52 will be provided

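### The only MMRM code in SAP 10.1 names the PP dataset, against the ITT text, and uses maximum likelihood, so Week 52 standard errors are about 2 to 2.5% too small at the planned size

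*SAP*

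**What the plan says.** On the population, the text is consistent:

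- The protocol synopsis says "Efficacy analyses will be primarily run on the intent-to-treat (ITT) population".
- Protocol 10.1.2 says "Efficacy analysis will be primarily based on the intent-to-treat (ITT) population".
- Protocol 10.6.1 says "All efficacy analysis will be primarily run on the ITT population and then they may be run on the PP population".
- SAP 10 says "Efficacy analyses will be performed on the ITT population".
- SAP 10.2 says "The analysis outlined in section 10.1 will be repeated using the PP population", which makes sense only if 10.1 is itself the ITT analysis.

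The model code in SAP 10.1, labelled as a sample, opens with "proc mixed data=pp method=ml". It is the only PROC MIXED block in the SAP. It sets an unstructured covariance matrix and has no degrees-of-freedom option. Neither document names an estimation method anywhere else.

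The model is fitted separately in each stage. The two Week 52 p-values then enter the Simes and weighted inverse-normal combination that decides superiority. SAP 10.2 adds a combined-stage fit: "An MMRM using the same model used in the primary analysis". SAP 10.3 reuses that fit for the secondary endpoints, and SAP 10.4 also specifies an MMRM. None of these sections names an estimator of its own.

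**The concern.** A programmer who follows the code would run the primary analysis on PP. The PP repeat in 10.2 would then be the same analysis, and no stage-wise ITT result would exist. PP is a materially different set. SAP 5.2 requires at least 8 infusions, no two consecutive missed infusions, baseline and post-baseline walk data, and no critical or major deviation bearing on the endpoint. Most of these conditions are judged on what happens after randomisation.

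ML estimates the covariance matrix as if the fitted means and slopes were known. The residual variance, and hence the standard error of the Week 52 difference, comes out too small. Both stage-wise p-values are then slightly too small, and so is the combined p-value, in an analysis whose stated purpose is to control the overall type I error.

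**Working it through.** **Planned sizes.** SAP 5.3 needs 99 subjects in Stage 1 and 66 in Stage 2, which is 33 per arm, and then states "To account for a 20% dropout rate, approximately 126 will be randomised into one of the three treatment arms (42 subject/arm) in Stage 1". Check: 33 / 0.8 = 41.25, rounded up to 42. Then 3 × 42 = 126 and 2 × 42 = 84, as the SAP has it. Dropout is therefore 42 − 33 = 9 per arm.

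**Closed-form approximation.** With N subjects and p mean parameters per visit (arm means plus the baseline and body-part slopes), the ML/REML standard error ratio is about √((N − p)/N).

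- Stage 1: √((126 − 5)/126) = 0.980, or 2.0% too small.
- Stage 2: √((84 − 4)/84) = 0.976, or 2.4% too small.

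**Fits of the SAP model.** Data were simulated and fitted by both ML and REML: four post-baseline visits, unstructured 4 × 4 covariance, treatment-by-visit means, and single baseline and body-part slopes. The SD of 11 m comes from SAP 5.3. Assumed: AR(1) correlation 0.7 and dropout completely at random. In each arm of 42, the numbers with 4, 3, 2, 1 and 0 visits observed were 33, 3, 2, 2 and 2.

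| Setting | Stage 1 ML/REML SE ratio | Stage 2 ML/REML SE ratio |
|---|---|---|
| 42 per arm, 9 dropping out | 0.980 | 0.978 |
| 33 per arm, complete | 0.978 | 0.975 |

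Exchangeable correlation of 0.7 moves the ratios by at most 0.002. A separate simulation at 42 per arm with 20% dropout, over other correlations (0.3 to 0.9), gave shortfalls of 1.9 to 2.1% in Stage 1 and 2.1 to 2.4% in Stage 2.

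**Type I error.** Each null trial had a three-arm Stage 1, dose selection by the SAP 5.4 conditional-power rule (with s taken as the SD), a two-arm Stage 2, and the SAP 10.1 combination with equal weights. There were 100,000 trials with dropout and 40,000 with 33 complete per arm. ML and REML tests used t on n − (arms + 2) degrees of freedom, with n the subjects in the fit.

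| Error rate | ML | REML | REML with Kenward-Roger |
|---|---|---|---|
| Stage 1 two-sided, with dropout | 5.6% | 5.1% | 5.0–5.1% |
| Stage 2 two-sided, with dropout | 5.7% | 5.2% | 5.0–5.1% |
| Overall one-sided, with dropout | 2.69% | 2.42% | 2.37% |
| Overall one-sided, 33 complete | 2.57% | 2.25% | 2.24% |

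Monte Carlo standard errors are 0.07 points for the stage-wise rows, 0.04 for the overall row with dropout and 0.06 for the last row. With a normal reference instead of t, overall error with dropout is 2.87% (ML) and 2.59% (REML).

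**At the threshold.** An overall one-sided p of 0.025 has z = 1.960. Multiplying by the mean ratio (0.980 + 0.978)/2 = 0.979 gives 1.919, so p = 0.0275. With the 33-complete ratios, (0.978 + 0.975)/2 = 0.9765 gives z = 1.914 and p = 0.0278. ML changes the overall conclusion in about 0.3% of null trials.

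**Power.** With 6 m added to both doses at Week 52, power is 91.3% with ML and 90.7% with REML.

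**Combined-stage MMRM.** The ratio is 0.987 to 0.989. Two-sided error is 5.3 to 5.4% with ML and 5.1% with REML.

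**The case against.** The code is labelled as a sample, and every governing sentence says ITT. An analyst working from the text would not report PP as primary. That stands as far as intent goes, and the dataset name is most likely left over from something else. But this is the only code supplied for the primary analysis, and it contradicts the text.

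ML is a recognised estimator, was written down in advance, and contradicts nothing in either document. This also stands: the objection to ML is small-sample bias, not inconsistency. The stage-wise errors of 5.6 to 5.7% are not the decision quantity, because no stage is tested alone for superiority. On the quantity that decides, the excess is 0.19 points over 2.5% with dropout. With 33 complete per arm, 2.57% cannot be told apart from nominal (simulation error 0.06). That limits how much weight the point should carry, but it gives no reason to keep ML, since REML costs almost nothing.

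The 2 to 2.5% figure rests on the planned size. SAP 2 reports early termination, and the documents give no final numbers. A smaller trial would have a larger shortfall: at an assumed 20 per arm, 3.6 to 4.2% in Stage 1 and 4.1 to 4.7% in Stage 2.

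**Conclusion.** The concern holds. Code and text disagree on the primary population, and the text makes clear that ITT is meant. As specified, the estimator understates the Week 52 standard error by 2.0% (Stage 1) and 2.2% (Stage 2) at the planned size with 20% dropout, and by 2.2% and 2.5% with 33 complete per arm. The effect on overall error is small and matters only for a result near the threshold.

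These figures assume an SD of 11 m, a within-subject correlation near 0.7, dropout completely at random and the planned numbers. The missing degrees-of-freedom option does not cause the shortfall; it only leaves the reference distribution to the software default. The correction should be made because it is cheap and affects the p-values that decide superiority.

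**What to change.** In SAP 10.1, change the opening line of the code to `proc mixed data=itt method=reml;`. In 10.2, state that the same code is run on the PP dataset as the sensitivity repeat. State that REML also applies to the combined-stage MMRMs in 10.2 to 10.4. Naming a small-sample degrees-of-freedom method, for example `ddfm=kr`, is a sensible addition: in the check it moved Stage 2 two-sided error from 5.2% to 5.05%.

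The cost is two tokens of code and a few sentences. The p-values become slightly larger, and power for 6 m falls by 91.3 − 90.7 = 0.6 points on the rounded figures. The change should be made before unblinding, so that neither the population nor the estimator is settled with results in hand. The documents do not show whether that is still possible. If it is not, report the change as post hoc and show the ML result beside it.
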